## MSSM Protocol Template HRP-503a

### Instructions:

1. Prepare a document with the following sections. Note that, depending on the nature of your research, certain sections below may not be applicable. Indicate N/A as appropriate, explaining where possible.
2. For any items described in the sponsor's protocol, grant application or other source documents submitted with the application, you may reference the title and page numbers of these documents rather than cutting and pasting into this document. **Do NOT refer to any derived documents, such as the Sample Consent document, or other internal documents required with the submission.**
3. If you reference page numbers, attach those pages to this protocol.
4. When you write a protocol, keep an electronic copy. You will need to modify this copy when making changes.

## Brief Summary of Research (250-400 words):

### 1) Objectives:

#### *Research Question:*

#### MAIN HYPOTHESES

1. IVIM, DCE-MRI and MRE metrics can non invasively discriminate severe fibrosis/cirrhosis (F3-F4), from no fibrosis (F0) and intermediate fibrosis (F1-F2). To test our hypothesis, we will prospectively determine in a cohort of 100 subjects (including 80 with chronic liver disease and 20 controls) whether IVIM DW-MRI, DCE-MRI and MRE parameters are valid markers of liver fibrosis, using histopathology from liver biopsy or explant as the reference.
2. MRI has equivalent performance to ultrasound elastography [including TE (transient elastography, Fibroscan) and ARFI (Acoustic Radiation Force Impulse imaging, Siemens) and serum markers for staging liver fibrosis, with the advantage of being more comprehensive and by providing whole liver coverage.

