## **b) Inclusion and Exclusion Criteria**

### **Inclusion criteria**

Study group

- 1) Chronic liver disease (including viral hepatitis, alcoholic hepatitis, non alcoholic steatohepatitis, primary biliary cirrhosis, primary sclerosing cholangitis, etc.)
- 2) 18 years of age and older
- 3) Patient is able to give informed consent for this study and agrees to provide a blood sample  
Patients preferably (but not necessarily) underwent/will undergo:
- 4) Liver biopsy (percutaneous or transjugular or surgical) performed within 6 months, as part of routine clinical care and/or
- 5) Liver transplant or liver resection performed as part of routine clinical care and/or
- 6) Medical therapy for portal hypertension or TIPS placement as part of routine clinical care and/or

Antiviral therapy for HCV infection.

Control group

- 1) Patients without history of liver disease and healthy volunteers
- 2) 18 years of age and older
- 3) Subject is able to give informed consent for this study and agrees to provide a blood sample

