### **Exclusion criteria**

1. Age less than 18 years
2. Unable or unwilling to give informed consent
3. Contra-indications to MRI
  - a. Electrical implants such as cardiac pacemakers or perfusion pumps
  - b. Ferromagnetic implants such as aneurysm clips, surgical clips, prostheses, artificial hearts, valves with steel parts, metal fragments, shrapnel, tattoos near the eye, or steel implants
  - c. Ferromagnetic objects such as jewelry or metal clips in clothing
  - d. Pregnant subjects
  - e. Pre-existing medical conditions including a likelihood of developing seizures or claustrophobic reactions.

As with all subjects referred for MRI, each subject is screened for possible contraindications with a routine questionnaire.

Subjects with GFR <30 will not undergo DCE-MRI with Gadolinium contrast. For subjects with GFR <30, we will still consider enrolling them for a non-contrast MR protocol, including non-contrast sequences, FibroScan and/or ARFI and blood tests. Subjects with GFR between 30 and

	Protocol Title:	Detection of Liver Fibrosis Using IVIM Diffusion and DCE MRI in HCV
	Principal Investigator Name/Contact Info:	[name]
	Primary Contact Name/Contact Info	[name] [contact] [contact]
	Date Revised:	9/16/2016
	Study Number:	GCO09-1187

60 will receive only either a half dose Multihance or Gadoxedate disodium (Eovist), and will not have repeat DCE-MRI studies with Gadolinium contrast. Only subjects with GFR  $\geq 60$  will be proposed to return for repeat DCE-MRI studies with Gadolinium contrast. Subjects with GFR  $< 60$  will be considered to return for repeat non-contrast MRI-studies.

We will consider injecting gadolinium contrast in healthy volunteers, for the purpose of DCE-MRI image optimization.

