### f) Procedures Involved in the Human Research

#### Visit 1

Blood test – GFR measurement to be done to evaluate renal insufficiency, liver serum markers, and pregnancy if applicable will be done for research - takes about 10 minutes. DW-MRI and DCE-MRI (MRI with intravenous contrast only if GFR>30) is standard of care and added MRE which is research will be 5 extra minutes (the entire MRI will take about 45 minutes)

Fibroscan and/or ARFI to determine liver stiffness will be done for research - takes about 10-20 minutes.

Visit 1 should take about 60-90 minutes.

Patients under medical treatment for portal hypertension or TIPS procedure are considered to be scheduled for visit 1 before they start their portal hypertension treatment or get TIPS placement.

#### Visit 2

DW-MRI and DCE-MRI (MRI with intravenous contrast only if GFR  $> 60$ ) with MRE sequences is done for research and done for reproducibility and will take another 45 minutes to complete to the first 30 subjects. This visit will take place within a week after visit 1.

This visit may have another blood test and another Fibroscan and/or ARFI so the entire visit should take about 60-90 minutes.

	Protocol Title:	Detection of Liver Fibrosis Using IVIM Diffusion and DCE MRI in HCV
	Principal Investigator Name/Contact Info:	[name]
	Primary Contact Name/Contact Info	[name] [contact] [contact]
	Date Revised:	9/16/2016
	Study Number:	GCO09-1187

Patients under medical treatment for portal hypertension or TIPS procedure are considered to be scheduled for visit 2 after they started their portal hypertension treatment or got TIPS placement to look at changes in hepatic flow and liver stiffness.

Patients starting antiviral therapy for HCV will be evaluated before they start the therapy, and will be repeated 3 to 6 months after the end of therapy.

We would like to perform the following sub-studies: All subjects will receive by default Gd-BOPTA (Multihance, Bracco) enhanced MRI (half dose at 0.05 mmol/Kg for the perfusion study) at 1.5T or 3T. In addition, the subjects may receive one of the following options:

**Option 1:** 1.5T MRI using (Gadoxedate disodium (Eovist)) will be performed in up to 10 subjects.

- Sub-arm 1: In up to 5 subjects receiving Gadoxedate disodium (Eovist), the studies will be repeated twice at least 24h apart to measure reproducibility of DCE-MRI using Gadoxedate disodium (Eovist)

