**Option 2:** 3T MRI using Gd-BOPTA (same dose as above), will be performed in up to 10 subjects. These could be different or same subjects as in option 1.

MR Elastography: Will be performed in all patients before contrast injection, using a 1.5 and/or 3T system (Siemens). The patient will be asked to perform multiple breath-holds during the image acquisition.

**Option 3:** Compare image quality and liver perfusion quantification between Cartesian and radial DCE-MRI acquisitions in a small subset of subjects (n=15), using the same contrast dose and MR system.

The liver explant analysis will be performed as part of routine clinical care. In addition, the following will be assessed: degree of biliary differentiation (by measuring semiquantitatively cytokeratin-19 expression).

Extra MRI sequences of the abdomen will be done for research.

Fibroscan and/or ARFI to determine liver stiffness will be done for research.

A blood test will be done to evaluate renal insufficiency, only if no recent EGFR value (not older than 6 weeks) is available in the medical record for contrast administration determination.

A blood test will be done to evaluate liver serum markers for research purposes.

A pregnancy test, if pregnancy cannot be excluded by women of child-bearing potential, will be performed prior to any scan to determine eligibility for study participation.

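### Does a 100-subject cohort for Hypothesis 1 conflict with the 250 subjects given in Section 5c?

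*Combined protocol and SAP*

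**What the plan says.** Section 1, Main Hypothesis 1, states: "we will prospectively determine in a cohort of 100 subjects (including 80 with chronic liver disease and 20 controls". The reference standard named there is histopathology from biopsy or explant. Section 5c gives 250 as the number of subjects and nothing else.

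Other sections show who may be enrolled beyond the histology cohort:

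- Section 5b introduces biopsy, transplant or resection, portal hypertension treatment and antiviral therapy with "Patients preferably (but not necessarily) underwent/will undergo". Histology is therefore not a condition of entry. One of the listed routes is "Medical therapy for portal hypertension or TIPS placement as part of routine clinical care".
- Section 5b, on subjects with GFR below 30, says that "we will still consider enrolling them for a non-contrast MR protocol". These subjects do not have DCE-MRI.
- Section 5f adds a before-and-after group: "Patients starting antiviral therapy for HCV will be evaluated before they start the therapy". Neither this group nor the portal hypertension group has a stated size.
- Section 5f gives sizes for the smaller exercises. The repeat visit for reproducibility applies "to complete to the first 30 subjects". Option 1 "will be performed in up to 10 subjects", Option 2 has the same ceiling, and Option 3 has 15 subjects. On Option 2 it adds: "These could be different or same subjects as in option 1".

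The supplied text has no sample-size justification, and states no alpha, power, target AUC, equivalence margin or dropout rate.

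**The concern.** Two totals that differ 2.5-fold (250/100), in one protocol, with no sentence joining them, suggest that one was updated and the other forgotten. If so, a reader could not tell whether the main accuracy results will rest on 80 patients or on every enrolled patient with histology.

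In an accuracy study the evaluable number sets the precision of sensitivity, specificity and AUC. Hypothesis 2 appears to use the same population, so it would be affected as well. There is also a question of selection: if more than 80 patients turn out to have histology and no rule says which are analysed, the set could in principle be chosen after imaging and histology are known. That would weaken the claim that accuracy is determined prospectively.

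**Working it through.** **1. The plan's own figures.** 80 + 20 = 100, so Hypothesis 1 is internally consistent. Section 5c gives 250. The difference is 250 − 100 = 150, and 100/250 = 40%.

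**2. Is 250 the 100 inflated for loss?** With n/(1 − d), losses of 10%, 20% and 30% give 112, 125 and 143. Reaching 250 needs d = 60%: 100/0.40 = 250. The documents state no loss rate, so ordinary attrition is not the link.

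**3. Do the numbered sub-studies account for the 150?** If none overlapped, 100 + 30 + 10 + 10 + 15 = 165, leaving 85. This sum is only an upper bound on the numbered groups. The repeat-visit subjects are the first ones enrolled, the options are extra scans for subjects already in the study, and Option 2 may reuse Option 1 subjects. The direct figure is the 150. Patients without histology and the two unsized treatment groups are candidates for it.

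**4. Can both numbers be true?** The share of patients with histology that yields 80 evaluable patients depends on the split of the 250, which is not stated. Two possibilities:

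| Assumed split of 250 | Share giving 80 | Evaluable if 60% have histology |
|---|---|---|
| 230 patients, 20 controls | 80/230 = 34.8% | 0.6 × 230 = 138 |
| 200 patients, 50 controls (4:1) | 80/200 = 40% | 0.6 × 200 = 120 |

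Since histology is optional at entry, a share of 35% to 40% is possible. A higher share gives more evaluable patients than planned.

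**5. What precision is at stake?** The documents give no AUC or stage mix, so these inputs are assumptions: AUC A = 0.85, 40% of patients F3-F4, patients only. The Hanley-McNeil standard error, with n1 patients F3-F4 and n2 others, is

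SE = √{[A(1 − A) + (n1 − 1)(q1 − A²) + (n2 − 1)(q2 − A²)]/(n1·n2)}, where q1 = A/(2 − A) = 0.7391 and q2 = 2A²/(1 + A) = 0.7811.

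| Patients with histology | n1 vs n2 | SE | 95% half-width (1.96 × SE) |
|---|---|---|---|
| 80 | 32 vs 48 | 0.0470 | 0.092 |
| 120 | 48 vs 72 | 0.0383 | 0.075 |
| 138 | 55 vs 83 | 0.0357 | 0.070 |
| 200 | 80 vs 120 | 0.0296 | 0.058 |

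Over AUC 0.80 to 0.90 and 30% to 50% F3-F4, the half-width runs from 0.071 to 0.116 with 80 patients and from 0.044 to 0.073 with 200. The 200-patient row requires every patient to have histology, which Section 5b does not. The 120 and 138 rows are the more realistic comparison: an improvement of about 0.02 on the 80-patient figure.

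**6. Who can be analysed?** A patient without biopsy or explant has no reference result and cannot contribute to accuracy against histology. A subject with GFR below 30 has no DCE-MRI and can contribute only to the non-contrast measures. Both conditions follow from the existing text without a separate rule.

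**The case for a change.** The strongest case for acting is that the relation between the numbers has to be inferred. No section says that the 100 is a subset of the 250, or whether it is a target, a cap or a minimum. The implied conditions in step 6 are not a written analysis-set definition, and controls have no histology criterion at all. The 6-month limit in Section 5b is attached to biopsy and not to transplant or resection. The template instructions let authors refer to a grant or sponsor protocol, but no supplied section does so for sample size. Clarifying this would cost only a few sentences.

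Those observations about the text are correct, and a sentence in Section 5c would help a reader. What does not stand is the step from a missing sentence to a defect in the plan. Sections 1 and 5c need not show the same number, because a hypothesis cohort and a protocol-wide enrolment figure are different quantities. Nothing in the text indicates that 250 replaced 100. A breakdown of the 250 by type of patient would not add up cleanly either, since the histology and portal hypertension routes are joined by and/or and one patient may follow several. As for selection, an analyst meeting more than 80 patients with histology would ordinarily use all of them. Nothing in the plan invites discarding any.

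**Conclusion.** The concern is right that the link between 100 and 250 is unwritten and that 150 subjects are not attributed. It does not show that either number is wrong, and no change is called for. The two figures are compatible if about 35% to 40% of patients have histology. If the share is higher, the analysis gains patients.

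No stated power, precision or decision rule depends on either total, so no calculation in the plan is undermined. The natural reading is to analyse every enrolled patient with evaluable MRI and histology, and to use subjects without DCE-MRI for the non-contrast measures only. On that reading, at a 60% histology share, the half-width for one AUC would be about 0.07 to 0.08, against 0.09 with 80 patients, so the ambiguity leans towards better precision than the 80-patient cohort gives.

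This rests on reading 250 as total enrolment. The patient/control splits, histology shares, AUC and stage mix are also assumed, because the documents give none of them.

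### Hypothesis 1 is to be tested in 100 subjects against histopathology, but the 20 controls have no planned histology and the patients need not have any, so at most 80 can have the stated reference

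*Combined protocol and SAP*

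**What the plan says.** Section 1, Main Hypothesis 1, sets the task as using MRI metrics to "discriminate severe fibrosis/cirrhosis (F3-F4), from no fibrosis (F0) and intermediate fibrosis (F1-F2"). It says the study will "prospectively determine in a cohort of 100 subjects (including 80 with chronic liver disease and 20 controls") whether the MRI metrics are valid, and names the reference once, for that whole cohort: "using histopathology from liver biopsy or explant as the reference".

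Section 5b defines the two groups.

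- **Controls** are "Patients without history of liver disease and healthy volunteers". Their other criteria are adult age, consent and a blood sample. No histology item appears.
- **Patients** have the histology items, for example "Liver biopsy (percutaneous or transjugular or surgical) performed within 6 months, as part of routine clinical care". The line above those items reads "Patients preferably (but not necessarily) underwent/will undergo". The same and/or list includes portal hypertension treatment, TIPS and antiviral therapy, none of which is a source of histology.

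Section 5f lists no biopsy as a study procedure. On explants it says "The liver explant analysis will be performed as part of routine clinical care".

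The purposes in Section 2 describe performance in patients with chronic liver disease compared with controls. They do not say what fibrosis stage a control is given or whether controls join the F3-F4 versus F0-F2 comparison. The document has no statistical analysis section and no sample-size calculation.

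**The concern.** The cohort size and the reference standard in Section 1 do not fit together. A subject without histology cannot be classified by the stated reference, and one fifth of the planned cohort has none planned. The size of 100 for a histology-referenced test therefore cannot be delivered as written.

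This matters because the gap has to be closed somehow at analysis, and the document does not say how. One natural way is to call the controls F0 and count them among the negatives. People without liver disease are likely to be easier to tell apart from F3-F4 than patients with F0-F2 disease are. The result would then be a blend of two comparisons, one of them easier. Sections 2 and 8 say the aim is fewer liver biopsies, and that decision arises in patients with liver disease. A blended figure would describe performance in a mixture that the test is not meant for.

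**Working it through.** **1. Check of the stated size.** 80 + 20 = 100, which agrees. No further derivation of 100 can be reproduced, because the documents give no expected accuracy, prevalence of F3-F4, power or precision target.

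**2. How many can have the stated reference.**

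| Group | Planned in Section 1 | Histology in Sections 5b and 5f | Maximum with reference |
|---|---|---|---|
| Chronic liver disease | 80 | Preferred, from routine care only | 80 |
| Controls | 20 | None planned | 0 |
| Total | 100 | | 80 |

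So 100 − 20 = 80 is a ceiling, with no stated minimum. For DCE metrics the number can fall further, because Section 5b allows subjects with GFR below 30 to enrol without contrast MRI.

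**3. Effect on the AUC if controls were pooled as F0.** These inputs are assumptions, not in the documents: histology in all 80 patients; a fraction f = 0.30-0.50 of them F3-F4; AUC 0.80-0.90 for F3-F4 against F0-F2 patients (A_p); AUC 0.95-1.00 for F3-F4 against controls (A_c).

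The pooled AUC is a pair-weighted mean. With n = 80(1 − f) negative patients:

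pooled AUC = (n·A_p + 20·A_c)/(n + 20), so shift = w·(A_c − A_p), with w = 20/(n + 20).

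| Case | f | n | w | A_p | A_c | Shift |
|---|---|---|---|---|---|---|
| Smallest | 0.30 | 56 | 20/76 = 0.263 | 0.90 | 0.95 | 0.263 × 0.05 = 0.013 |
| Central | 0.40 | 48 | 20/68 = 0.294 | 0.85 | 0.98 | 0.294 × 0.13 = 0.038 |
| Largest | 0.50 | 40 | 20/60 = 0.333 | 0.80 | 1.00 | 0.333 × 0.20 = 0.067 |

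In the central case the pooled AUC is (48 × 0.85 + 20 × 0.98)/68 = 0.888 instead of 0.850.

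**4. Effect of pooling on the interval.** In a binormal simulation of the central case (20,000 runs; 32 F3-F4, 48 F0-F2 patients, 20 controls), 1.96 × SD of the AUC is 0.084 in patients only and 0.063 pooled. Most of that narrowing comes from the assumed 0.98. With 0.85 against controls as well, the change is only from about 0.084 to 0.079. The Hanley-McNeil formula at AUC 0.85 shows the same: 0.092 for 32 versus 48 and 0.090 for 32 versus 68.

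**5. Effect of incomplete histology in patients.** Hanley-McNeil 95% half-width at AUC 0.85 with 40% F3-F4 (both assumed):

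| Patients with histology | F3-F4 vs F0-F2 | Half-width |
|---|---|---|
| 80 | 32 vs 48 | 0.092 |
| 60 | 24 vs 36 | 0.107 |
| 40 | 16 vs 24 | 0.131 |

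On these figures, falling short of 80 patients with histology costs more precision than leaving out the controls.

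**The case against.** The strongest reply is that no pooled analysis is planned. The document names no AUC, no ROC method and no pooling rule. The purposes in Section 2 set controls beside patients as a comparison group, and that reading is close to reporting them separately. This stands. A reader might infer from Section 1 that the controls are to be counted as F0, or can enter in no other way, but the text does not say so. The bias in step 3 is conditional on pooling. What the reply does not remove is the mismatch in Section 1, where one reference is stated for a cohort of which 20 members have no planned source for it.

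A second reply is that taking people without liver disease as F0 is a reasonable convention. It may be, but the protocol does not adopt it, and it is a different reference from the one stated. A control may happen to have surgical histology, but none is planned.

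A third is that histology may come from more subjects than these, since Section 5c gives 250. The ceiling of 80 does apply only to the 100-subject cohort of Hypothesis 1. A reader might see 100 and 250 as a contradiction. They are compatible if 250 is total enrolment, and the document describes sub-studies and volunteers scanned for image optimisation. The missing link between the two numbers is a side note.

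**Conclusion.** The mismatch is established from the text alone: at most 80 of the 100 can be tested against the stated reference. It would be tempting to read 80 as the number that will have histology. The documents do not support that, because histology is optional in patients and no minimum is given.

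The size of the possible bias is less certain. If controls were pooled as presumed F0, the AUC would rise by about 0.013 to 0.067 (0.038 in the central case) under the assumed prevalence and AUCs. The direction needs only that controls are easier to separate from F3-F4 than F0-F2 patients are. An apparently tighter interval is not a firm part of the conclusion, because it depends mostly on how high the AUC against controls is assumed to be. The point should be fixed, and a change of wording is enough.

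**What to change.** In Section 1, restate the histology-referenced cohort for Hypothesis 1 as the patients with chronic liver disease who have histopathology. Say that this is at most 80 of the 100, and have the sponsor state the target number. Make F3-F4 versus F0-F2 in those patients the main analysis.

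Report the 20 controls separately as a normal comparison group. If a pooled analysis is also wanted, label it secondary and state that F0 is presumed in controls.

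Optionally, add a sentence to Section 5c saying how 250 relates to the 100.

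The cost is protocol wording. It needs no biopsy of controls and no change to eligibility. Compared with a pooled analysis, the main estimate would probably be lower (by 0.013 to 0.067 under the assumptions above) and its interval somewhat wider. If the sponsor's target cannot be met with histology optional, the shortfall will at least be visible.
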